11.7	Provisions to Protect the Privacy Interests of Subjects	
11.8	Record Retention	
11.9	Obligations of Investigators	
12.0	REFERENCES	

2022

LIST OF ABBREVIATIONS

ΑE Adverse Event

ALC Absolute Lymphocyte Count ALT Alanine Aminotransferase AST Aspartate Aminotransferase BAT **Basophil Activation Test** BTK Bruton's Tyrosine Kinase BUN Blood Urea Nitrogen CBC Complete Blood Count

CLL Chronic Lymphocytic Leukemia CMP Comprehensive Metabolic Panel

CRU Clinical Research Unit

SBPC Single-blind Placebo-controlled

DLT **Dose-Limiting Toxicity**

DSMB Data and Safety Monitoring Board

EKG Electrocardiogram FC Food Challenge

H&P History & Physical Exam

HRPP Human Research Protections Program

ΙgΕ Immunoglobulin E IV (or iv) Intravenously

MCL Mantle Cell Lymphoma MTD Maximum Tolerated Dose OFC Oral Food Challenge

PBMCs Peripheral Blood Mononuclear Cells

per os/by mouth/orally p.o. PST Peripheral Blood Testing SAE Serious Adverse Event Surface Immunoglobulin E slgE

SGOT Serum Glutamic Oxaloacetic Transaminase **SPGT** Serum Glutamic Pyruvic Transaminase

SPT Skin Prick Test **WBC** White Blood Cells

WM Waldenstrom's Macroglobulineia

This is a phase II open label study involving the use of acalabrutinib to prevent food-induced anaphylaxis in adults with food allergy. Acalabrutinib (brand name Calquence®; manufacturer AstraZeneca [AZ]) is currently FDA approved for the treatment of mantle cell lymphoma (MCL). We propose to administer this approved drug to adults with food allergy to inhibit anaphylaxis.

STUDY SCHEMA

This is an open-label study designed to determine the ability of acalabrutinib to prevent signs and symptoms of anaphylaxis during a food challenge in food-allergic subjects.

At Visit 1, after undergoing informed consent, subjects will undergo procedures for assessment of baseline status and eligibility (clinical history and skin prick test ISPT) to peanut and/or tree nuts as well as histamine and saline SPT positive and negative controls, respectively). After eligibility is confirmed, subjects will undergo a single-blind, placebo-controlled graded food challenge (SBPCFC) of up to 4 g of peanut or tree nut protein, administered over escalating doses while being monitored in a clinical research unit (CRU) setting. Prior to the SBPCFC, 30 mL of peripheral blood will be collected for basophil activation testing (BAT), serum specific IqE to peanut/tree nuts and components, as well as toxicity lab testing monitoring. During the food challenge, subjects will be assessed for signs and symptoms of foodinduced anaphylaxis between each dose per food challenge protocol, upon report of any symptoms and should any objective change in clinical status occur. Once a confirmed reaction occurs, the food challenge will be terminated and the reaction treated until it has resolved. Subjects will be discharged from the CRU no sooner than 2 hours after completion of the food challenge. They may be observed longer should a reaction occur at the investigator's discretion. Additional blood will be drawn at fixed intervals for biomarkers of anaphylaxis including mast cell and basophil microparticle analysis. This visit will establish each subject's baseline threshold dose for peanut/tree nut reactivity.

After a minimum of a two-week recovery period, subjects will be given acalabrutinib (four doses of 100 mg of acalabrutinib to be taken orally twice daily) and return for Visit 2 to undergo repeat SPT, SBPCFC, and phlebotomy in an identical manner to Visit 1 to establish each subject's new threshold dose for peanut/tree nut reactivity while on acalabrutinib, which we hypothesize will be higher. At this point of the protocol, acalabrutinib dosing will be stopped. Follow up visits for up to 6 months after cessation of acalabrutinib will be conducted to repeat toxicity labs and skin testing.

At each visit, subjects will be monitored for toxicities, including CBC w/diff, CMP, and pregnancy testing. Prior to drug initiation and at the end of the trial, an EKG will be performed.

STUDY SUMMARY

Title	Preventing Life-Threatening Allergic Reactions with Acalabrutinib, an FDA-Approved BTK Inhibitor			
Protocol Number	MD12042018			
Phase	Phase 2			
Methodology	Open label study to determine efficacy and safety of acalabrutinib for the treatment of food allergy			
Study Duration	14 weeks			
Study Center(s)	Single-center			
Objectives	Primary: To determine the ability of acalabrutinib to 1) suppress food skin prick test size and 2) prevent food-induced anaphylaxis and/or shift the threshold dose of food at which a food allergic subject will react to a higher level. Secondary: To determine if blood mast cell and basophil microparticles can be utilized as markers for anaphylaxis.			
Number of Subjects	10			
rianison or cabjeolo	10			

PROTOCOL: MD12042018 2022

Diagnosis and Main Adults with history of food allergy to peanut and/or tree nut will be invited.

Version: February 9,

Inclusion Criteria	to participate.			
Study Product(s), Dose, Route, Regimen	Acalabrutinib 100 mg, PO twice daily			
Duration of administration	2 days			
Reference therapy	There are currently no approved therapies for food allergy			
Statistical Methodology	Primary efficacy endpoint: Change in highest tolerated dose of the food allergen. This endpoint will be analyzed by paired Student's t test. Secondary efficacy endpoints will include: 1. change in severity of reaction during food challenge 2. change in skin prick test wheal size 3. change in BAT percent activation			

1.0 **BACKGROUND AND RATIONALE**

1.1 **Disease Background**

Food allergy is a potentially life-threatening disease, and its prevalence continues to increase despite public health efforts (1, 2). Newer studies have shown that it is less likely that affected persons will develop natural tolerance over time, and food allergies can also develop in adulthood, so more adults now have potentially life-threatening food allergies. Severe and near fatal reactions can occur and can lead to devastating outcomes, including fatalities (3). Furthermore, the economic burden of childhood food allergy is nearly \$25 billion per year, with as many as 200,000 emergency department visits annually (4). Despite this significant disease burden, there are currently no approved therapies for food allergy. Standard of care is constant vigilance in avoidance of allergen, and use of self-injected epinephrine after a reaction has occurred. Therefore, there is a large unmet need for new therapeutics to prevent food-induced anaphylaxis. FDA approved Bruton's tyrosine kinase (BTK) inhibitors such as ibrutinib. acalabrutinib and others under development (5, 6) may be able to fill this void and offer a therapy to these patients.

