2.0 STUDY OBJECTIVES

2.1 **Primary Objective**

2.1.1 To determine if short term administration of acalabrutinib to adults with peanut or tree nut allergy will reduce allergen skin test reactions and raise oral challenge thresholds

2.2 **Secondary Objectives**

- 2.2.1 To describe frequency and severity of the adverse events associated with acalabrutinib when administered in a short course of 2 days
- 2.2.2 To determine if 2 days of acalabrutinib have any impact on blood levels of total and food-specific IqE, and numbers of circulating eosinophils and basophils.

2.3 **Endpoints**

Primary Objective 2.1.1: The highest dose of food allergen that is tolerated (i.e. does not cause an objective clinical reaction) during a SBPCFC both before and while taking acalabrutinib, as defined by objective clinical findings on physical exam before/after each dose of food ingested using a published graded scoring system (15). Secondary endpoints include change in severity of clinical reaction as defined above SPT wheal size as defined by a decrease in wheal and/or flare diameter of skin prick tests to peanut/tree

2022

nut extracts, and percent activation of basophils from BAT as assessed by the percent of basophils with CD63 surface upregulation by flow cytometry.

Version: February 9,

Secondary Objective 2.2.1: Adverse events, including bleeding, cytopenias, hepatotoxicity, and renal toxicity will be monitored using laboratory testing and clinical exam as outlined in Section 4.2.

Secondary Objective 2.2.2: Change in blood levels of total and food-specific IgE, and numbers of circulating eosinophils and basophils as assessed by laboratory testing of peripheral blood samples.

Exploratory Objective: Peripheral blood will be analyzed for mast cell and basophil microparticles before, during, and after SBPCFC.

SUBJECT ELIGIBILITY 3.0

Subjects must meet all of the inclusion and exclusion criteria to be enrolled in the study. Study procedures may not begin until a subject has signed the informed consent form.

3.1 **Inclusion Criteria**

- 3.1.1 History of IgE-mediated food allergy to peanut or tree nut.
- 3.1.2 Male or female age ≥ 18 years.
- 3.1.3 Positive skin prick test to the trigger food(s), either peanut and/or tree nut(s).
- 3.1.4 Objective clinical reaction to 1,044 mg or less of the food allergen during baseline oral food challenge
- 3.1.5 Adequate organ and marrow function as defined below:

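### Criterion 3.1.4 settles ineligibility at 1,044 mg, but the Visit 1 challenge may run to 4 g and no visible stop is tied to the entry limit

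*Combined protocol and SAP*

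**What the plan says.** Section 3.1.4 of the protocol lists as an inclusion criterion: "Objective clinical reaction to 1,044 mg or less of the food allergen during baseline oral food challenge". Section 3.0 makes every criterion binding: "Subjects must meet all of the inclusion and exclusion criteria to be enrolled in the study". The figure of 1,044 mg appears nowhere else.

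The Study Schema sets the Visit 1 challenge as "SBPCFC) of up to 4 g of peanut or tree nut protein, administered over escalating doses". It ends that challenge on a reaction: "Once a confirmed reaction occurs, the food challenge will be terminated". Section 5.2.1 gives a second stop, also reaction-based, when clear objective symptoms appear. It lets the physician lengthen the interval between doses and requires at least 2 hours of observation after the last dose. No dose ladder is printed. The schema refers to assessments "between each dose per food challenge protocol", and Section 5.2.1 cites published procedures.

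The schema says the visit will establish each subject's "baseline threshold dose for peanut/tree nut reactivity". At Visit 2, subjects are to have "repeat SPT, SBPCFC, and phlebotomy in an identical manner to Visit 1", so the 4 g ceiling carries over to the on-treatment challenge.

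**The concern.** Criterion 3.1.4 is decided partway through a procedure that has a higher ceiling. Once a subject has taken the limit amount and been observed without an objective reaction, the entry question is answered: that person cannot go on to acalabrutinib or to Visit 2. Nothing in the visible text tells staff to stop there. The stated ceiling and the aim of finding a baseline threshold both point towards continuing.

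What is at stake is avoidable exposure. An adult with a history of peanut or tree nut allergy could be taken to a provoked reaction after the study has lost its use for the result. Section 5.2.1 already withholds the challenge when laboratory tests or the EKG are not within normal limits, so the protocol accepts the principle that a failed entry check ends allergen dosing. Criterion 3.1.4 has no matching rule.

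**Working it through.** **1. Stops on Visit 1 dosing, side by side**

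- Study Schema: a confirmed reaction ends the challenge.
- Section 5.2.1: clear objective symptoms end the challenge.
- Section 5.2.1, physician discretion: applies to the dosing interval.
- Section 5.5: the investigator may withdraw a subject; this is discretionary and not linked to 1,044 mg.
- Study Schema: a 4 g ceiling.

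The ceiling is the only limit on amount, and it lies above the entry limit.

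**2. Size of the gap**

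Inputs: entry limit 1,044 mg (Section 3.1.4); ceiling 4 g = 4,000 mg (Study Schema). Assumption: both are cumulative amounts of protein. The ceiling is given as protein. The limit is given only as an amount of the food allergen, and neither figure is labelled as single-dose or cumulative.

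- Further amount: 4,000 − 1,044 = 2,956 mg.
- Total relative to the limit: 4,000 / 1,044 = 3.83.
- On the log scale: ln(3.83) = 1.343. Section 10.2 equates one dose escalation with 1.1 natural log units, so this is 1.343 / 1.1 = 1.22 steps.

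**3. What the extra doses could contribute**

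- Primary endpoint: the SAP (Study Design and Endpoints) assesses it at Visits 1 and 2. An ineligible subject has no Visit 2, so contributes nothing.
- Safety analysis: Section 6.1 covers subjects who took at least one dose of study drug. An ineligible subject took none.
- Microparticles: Section 5.2.1 lists the analysis at Visit 1, but no text says whether samples from ineligible subjects would be used.

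**4. Effect of a Visit 1 stop on sample size and power**

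Section 10.2 and the SAP state 80% power with 10 subjects, a mean difference of 1.1 and a standard deviation of 1.1 natural log units, paired t test, p < 0.05. Taking the test as two-sided (not stated):

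- Noncentrality: √10 × 1.1 / 1.1 = 3.16, with 9 degrees of freedom.
- Exact power from the noncentral t distribution: 80.3%. The stated figure reproduces, and 10 is the smallest n that reaches 80%.

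A stop at the limit, placed on the scale that 3.1.4 uses, removes only doses given to people who could not be among the 10. N and power stay as they are.

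**5. Why the 4 g ceiling must stay at Visit 2**

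A subject who first reacts at 1,044 mg at baseline needs room above that amount to show a gain. The planned effect is one 3-fold step, and step 2 shows that 4 g leaves 1.22 steps. Carrying the Visit 1 stop over to Visit 2 would remove that room.

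**The case against.** The strongest reply is that the dose ladder and stopping rules are delegated to a food challenge protocol and published procedures that are not visible here, and these may already end the challenge at the limit. A 4 g maximum is not an instruction to reach it. This stands, and it limits the point to what the visible text permits. It does not remove the point: 1,044 mg is this study's own entry criterion, so the matching stop belongs in this protocol.

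A full baseline challenge is also a defensible choice. It gives the person an exact threshold, and a reaction above the limit might inform the microparticle objective. These are real losses under the fix, but the protocol states neither as a purpose for ineligible subjects.

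The risk is managed: intravenous access, emergency drugs at hand, experienced supervision and observation (Section 5.2.1), and exclusion of people with the most severe past anaphylaxis (3.2.8). This lowers the risk without making the exposure useful.

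Three stronger readings are tempting, and the documents do not support them:

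- That the protocol orders ineligible subjects to be dosed to 4 g. It is silent on what happens at 1,044 mg.
- That the primary analysis is biased or underpowered. If 3.1.4 is applied, these subjects never enter it.
- That the schema contradicts itself by placing the challenge "After eligibility is confirmed, subjects will undergo a single-blind, placebo-controlled graded food challenge". The schema names clinical history and skin prick testing as the eligibility checks just before this, so the phrase can be read as covering those alone.

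**Conclusion.** The point holds as a gap in the written procedure and an inexpensive safety improvement. The visible text makes a subject ineligible at 1,044 mg and leaves the same challenge open to 4 g. The possible excess is up to 2,956 mg, a total 3.8 times the limit, on the assumption that both figures are cumulative protein; another scale would change that figure. How many subjects would be affected cannot be derived from the documents and may be none. The conclusion also assumes that the unseen challenge procedure contains no stop at the limit. It concerns exposure of people who cannot be enrolled, and has no consequence for the primary result, the sample size or the power.

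**What to change.** In the Study Schema and Section 5.2.1:

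- End Visit 1 dosing at the 1,044 mg limit, on the same scale as 3.1.4.
- Record a screen failure if no objective reaction has occurred by the end of the existing observation period.
- State for both 1,044 mg and 4 g whether the amount is cumulative or a single dose, and for the 1,044 mg limit whether it is protein or food weight.
- Keep the 4 g ceiling for Visit 2, and except the ceiling from the requirement that Visit 2 repeat Visit 1.

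The cost is a few sentences of text. For ineligible subjects only, the exact threshold, the clinical information from a full challenge and possible microparticle samples are lost. Settle the scale before the stop is written: a stop on the wrong scale, for example a cumulative stop when 3.1.4 means a single dose, could end dosing too early and lose subjects who would have qualified. On the right scale, subjects who react at or before the limit dose have the same Visit 1 dosing as now.

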10.1 Study Design/Study Endpoints

This is an open label study of acalabrutinib in 10 food-allergic adults to determine the effect of pretreatment with acalabrutinib on food allergen reactivity in food-allergic subjects given acalabrutinib 100 mg twice daily for 2 days. The primary endpoint is the threshold dose of food at which a subject reacts before (at baseline) and after acalabrutinib therapy. Given the nature of the study, it will be stopped if 2 or more patients have a DLT.

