10.2 Sample Size and Accrual

10 subjects allows for 80% power to detect a 3-fold increase (1.1 natural log units; i.e. 1 food dose escalation) in the threshold food dose assuming that difference in threshold from post to pre is normally distributed with a standard deviation of 1.1 natural log units using a paired t test with p<0.05 as an approximation (though non-parametric tests will be utilized in the final analysis if needed). Patients will be recruited from the allergy clinics at Johns Hopkins University with a diagnosis of peanut (or tree nut) allergy by a boardcertified allergist-immunologist.

10.3 **Data Analysis**

As this is an open label trial, descriptive statistics will be used. If appropriate, the primary outcome variable of threshold dose will be log transformed, and a paired t test will be used. If assumptions for paired t test are violated, a Wilcoxon non-parametric sign test will be used. Each patient will be compared to him/herself prior to beginning treatment and at each time point in the study to assess SPT size, BAT response, and food challenge dose threshold and response. Similar methodologies will be used for analysis of adverse events.

STUDY MANAGEMENT 11.0

11.1 **Conflict of Interest**

Any investigator who has a conflict of interest with this study (patent ownership, royalties, or financial gain greater than the minimum allowable by their institution, etc.) must have the conflict reviewed Johns Hopkins University. All investigators will follow the University conflict of interest policy.

Institutional Review Board (IRB) Approval and Consent 11.2

It is expected that the IRB will have the proper representation and function in accordance with federally mandated regulations. The IRB should approve the consent form and protocol.

In obtaining and documenting informed consent, the investigator should comply with the applicable regulatory requirement(s), and should adhere to Good Clinical Practice (GCP) and to ethical principles that have their origin in the Declaration of Helsinki.

participate in the study by signing an IRB-approved consent form.

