Appendix 1: Pill Diary

		монтн				
Sunday	Monday	Tuesday	Wednesday	Thursday	Friday	Saturday
Н	4					
-						L
		L				L

The study coordinator will fill in the month and days.

Please document number of pills and time you took the ibrutinib.

STATISTICAL ANALYSIS PLAN

Study Design and Endpoints

This is an open label study of acalabrutinib in 10 food-allergic adults to determine the effect of pretreatment (100 mg twice daily for 4 doses total) with acalabrutinib on food allergen reactivity in foodallergic subjects. There are 3 planned study visits where endpoint assessments will be collected. The primary endpoint will be assessed at Visit 1 (baseline) and Visit 2 (after acalabrutinib). Secondary and exploratory endpoints will be assessed at Visits 1, 2, and 3 (follow-up).

Primary endpoint: Change in subjects' threshold dose of peanut protein to elicit an objective clinical reaction

Secondary endpoints:

- 1. Change in size of skin prick test wheal
- 2. Change in percent of ex vivo basophil activation to anti-IgE and peanut, as determined by CD63 expression

Safety considerations and toxicity monitoring: Laboratory testing (complete blood counts, serum chemistries) and electrocardiogram

Given the nature of the study, it will be stopped if >50% of patients have a DLT as described in the protocol.

Sample Size and Power Analysis

Sample size was calculated based on the primary endpoint, assuming that the difference in threshold from baseline to after acalabrutinib is normally distributed with a standard deviation of 1.1 natural log units. Therefore, 10 subjects allows for 80% power to detect a 3-fold increase (1.1 natural log units; i.e. 1 food dose escalation) in the threshold food dose, using a paired t test with p<0.05 as an approximation. though non-parametric tests will be utilized in the final analysis if needed.

Data Analysis

As this is an open label trial, each subject's responsiveness will be examined compared to themselves (at baseline) prior to initiation of treatment. Descriptive statistics will be used to analyze endpoints. The primary endpoint will be analyzed by log transformation and paired t test with p value < 0.05, if appropriate. If assumptions for paired t test are violated, a Wilcoxon non-parametric sign test will be used.

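### A subject who finishes the 4 g challenge on drug has a change known only as a lower bound; the plan has no rule for this, so any fold-rise it describes would be biased low if many finish

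*Combined protocol and SAP*

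**What the plan says.** **The cap.** The Study Schema describes a "graded food challenge (SBPCFC) of up to 4 g of peanut or tree nut protein", and has Visit 2 run "in an identical manner to Visit 1 to establish each subject's new threshold dose". The on-drug challenge therefore ends at 4 g as well. Inclusion criterion 3.1.4 requires an "Objective clinical reaction to 1,044 mg or less of the food allergen during baseline oral food challenge", so every enrolled subject has an observed baseline reaction.

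**The endpoint.** Two definitions are in use. The Study Summary has "Change in highest tolerated dose of the food allergen. This endpoint will be analyzed by paired" Student's t test, and section 2.3 also uses the highest tolerated dose. Section 10.1 instead states "The primary endpoint is the threshold dose of food at which a subject reacts before (at baseline) and after acalabrutinib therapy", and the SAP (Study Design and Endpoints) has "Change in subjects' threshold dose of peanut protein to elicit an objective clinical reaction".

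**The analysis.** Section 10.3 and the SAP (Data Analysis) plan descriptive statistics and, where suitable, a log transformation with a paired t test at 0.05. A Wilcoxon/sign test is the fallback. Section 10.2 sizes the trial "assuming that difference in threshold from post to pre is normally distributed with a standard deviation of 1.1 natural log units". Nothing in either document gives the value of a subject who finishes 4 g without reacting, and censoring is not mentioned.

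**The concern.** Finishing the challenge is not a corner case. Preventing the reaction is part of the primary objective in the Study Summary. Section 1.3 reports that a related BTK inhibitor made anti-IgE basophil activation negative in all subjects and 44% of skin tests negative.

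A finisher's true change is at least ln(4 g / baseline), and how far above is unknown. Entered as an exact value, it makes the recorded change depend on where the subject started: two equally protected subjects show different rises because one reacted at a low dose at baseline and the other near 1,044 mg. If everyone finishes, the mean and SD of the recorded changes describe who was enrolled and where the challenge stopped.

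At stake is the size of the effect and its uncertainty, which a reader would carry into the next trial. Whether there is any rise at all is not in doubt on this account.

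**Working it through.** **Inputs.** From the documents: cap 4,000 mg (Study Schema); highest admissible baseline reaction dose 1,044 mg (3.1.4); n = 10, SD 1.1 ln units, planned rise 3-fold = 1.1 ln units = one dose step (10.2). Assumed: all baselines below 1,044 mg, and the dose ladder, which the documents do not list.

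**1. The plan's power.** Paired t test, 9 df, noncentrality √10 × 1.1/1.1 = 3.16, two-sided 0.05 (sidedness is not stated): power 80.3%. The stated 80% is reproduced.

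**2. Largest recordable rise.** This is 4,000/B, where B is the baseline value. Under the eliciting-dose definition B is the reaction dose, with a finisher entered at 4 g. Under the tolerated-dose definition B is one 3-fold step lower.

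| Baseline reaction dose | Eliciting dose | Tolerated dose |
|---|---|---|
| 1,044 mg | 3.83-fold (ln 1.34) | 11.5-fold (ln 2.44) |
| 348 mg | 11.5-fold (2.44) | 34-fold (3.54) |
| 116 mg | 34-fold (3.54) | 103-fold (4.64) |
| 38.7 mg | 103-fold (4.64) | 310-fold (5.74) |

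**3. Everyone finishes.** The mean change is the mean of the ceilings. With these four baselines in equal shares:
- tolerated dose: (2.44 + 3.54 + 4.64 + 5.74)/4 = 4.09, about 60-fold;
- eliciting dose: (1.34 + 2.44 + 3.54 + 4.64)/4 = 2.99, about 20-fold.

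If all ten subjects reacted at 1,044 mg, the result is 11.5-fold or 3.83-fold with an SD of zero.

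**4. Intermediate effects.** Simulated trials of 10, recorded change = min(N(μ, 1.1), ceiling), the four baselines equally likely, ordinary t interval. Lowering every ceiling by one step is equivalent to raising the true effect by one step and then subtracting 1.1. Each eliciting-dose result is therefore the tolerated-dose result one row down, divided by 3.

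| True rise | Tolerated dose: estimate, coverage | Eliciting dose: estimate, coverage |
|---|---|---|
| 3-fold | 2.9-fold, 95% | 8.2/3 = 2.7-fold, 94% |
| 9-fold | 8.2-fold, 94% | exp(2.95 − 1.10) = 6.4-fold, 80% |
| 27-fold | 19-fold, 80% | about 12-fold, 35% |
| 81-fold | 35-fold, 35% | not needed here |

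**5. Other assumed baseline mixes** (ceiling 4,000/B; figures are estimated fold-rises).

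| Baselines (mg) | True 3 | True 10 (coverage) | True 30 | All finish |
|---|---|---|---|---|
| 1,044 ×10 | 2.2 | 3.4 (0%) | 3.8 | 3.83 |
| 444 ×5, 1,044 ×5 | 2.4 | 4.6 (0%) | 5.6 | 5.9 |
| 44 ×2, 144 ×3, 444 ×3, 1,044 ×2 | 2.7 | 6.7 (78%) | 11.5 | 16.9 |
| 14 ×3, 44 ×4, 144 ×3 | 3.0 | 9.7 (95%) | 25.0 | 89.8 |

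At a true 3-fold rise, 41%, 29%, 14% and 1% of subjects in these mixes are at the cap, and interval coverage is 86%, 93%, 95% and 95%.

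**6. The test itself.** With no effect, the upper-tail rejection rate in these mixes stays at about 2.5%. At 3-fold, power is 78% to 81%, against 80% without a cap. If all ten changes are positive, the exact sign or signed-rank p value is 2 × 0.5^10 = 0.002.

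**7. Does a censored model recover the size?**
- In the third mix of step 5, a right-censored normal model gives medians of 9.8-fold (true 10) and 28.0-fold (true 30), against about 6.7 and 11.5 for the capped mean.
- In the 444/1,044 mg mix it gives 9.0 (true 10), against 4.6. At a true 30-fold rise, about 82% of trials there have fewer than two subjects who react, and no fold-rise can be estimated.
- Under the step 4 assumptions (tolerated dose), a Wald interval from this model covers only about 90% at 9-fold. A profile-likelihood interval with a t cutoff covers 95% to 97% in trials with at least three reactors.

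**The case against.** Several points on the other side are sound.

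- **No fold-rise interval is planned.** The documents name descriptive statistics and a test, so a reader should not infer that the plan commits itself to a biased confidence interval. That stands. But descriptive statistics on change in threshold will carry the same capped values.
- **No text scores a finisher as exactly 4 g.** A reader might infer that there is such a rule. There is none; it is what a paired t test on the highest tolerated dose does in practice.
- **The highest dose tolerated during a challenge is bounded by design, so 4 g is its observed value.** That is a fair reading of section 2.3. It does not help under the eliciting-dose wording of section 10.1 and the SAP, where a finisher has no value, nor when the result is read as how far the drug moved the threshold.
- **The fallback test covers non-normal differences.** It protects the p value. It supplies no fold-rise that allows for the cap.
- **Large bias needs effects well beyond the design.** Under the tolerated-dose assumptions this is true: at 3-fold and 9-fold the bias is trivial. It is less true with eliciting-dose baselines or with baselines near 1,044 mg.
- **The figures rest on an assumed ladder.** They do. Since 4,000/1,044 = 3.83, a strict 3-fold ladder through 1,044 mg does not even land on 4 g.
- **Graded doses make every threshold interval-censored.** Correct, and the simulation ignores it. For a subject who reacts, the gap is one step. For a finisher it has no upper limit.

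**Conclusion.** The concern holds for the size of the effect. The 4 g cap, the absence of a rule for finishers and the two endpoint definitions are facts of the documents. How much they matter depends on how many subjects finish and on their baselines, neither of which the documents fix.

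It would be wrong to conclude that the primary test is invalid or the power claim mistaken: type I error and power hardly change, and the 80% is reproduced. Nor do the figures support discarding the t-based mean whenever anyone finishes. Under the tolerated-dose assumptions, about 76% of trials at a true 9-fold rise have at least one finisher, yet the t interval still covers 94%.

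What remains is that if the drug prevents the reaction in many subjects, as the trial hopes, an unqualified mean fold-rise would understate the effect and reflect the cap and the enrolled baselines. The 27-fold example (reported as 19-fold or 12-fold depending only on the endpoint definition) shows the direction and possible scale. It is not a forecast.

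**What to change.** Amend the SAP before the data are analysed:

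1. Use one endpoint definition in the Study Summary, sections 2.3 and 10.1, and the SAP.
2. State that a subject who finishes Visit 2 without reacting enters the primary paired test at the top dose. Keep the Wilcoxon/sign fallback as planned.
3. Report the number who finish 4 g.
4. For the size of the effect, treat finishers as right-censored at 4 g and give a censored-normal estimate of the mean log change with a profile-likelihood interval (t cutoff). Label any t-based mean fold-rise as a lower bound when anyone finishes.
5. If about half or more finish, report only the number of finishers and the median change as at least x-fold. No recorded change exceeds the true one, so the recorded median cannot exceed the true median of the sample.

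The cost is a few SAP sentences, aligned endpoint wording in the protocol, and one extra analysis of data already collected. No visit, procedure or sample size changes. The drawback is that intervals will be wide with 10 subjects, and if most finish only a lower bound can be stated.
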